**Table 3: Criteria for Potentially Clinically Significant Laboratory Values**

Test	Criterion value
Serum chemistry	
ALT	≥3x ULN
AST	≥3x ULN
ALP	≥3x ULN
GGT	≥3x ULN
LDH	≥3x ULN
BUN	≥10.71 mmol/L
Creatinine	≥177 μmol/L
Uric acid	Men
	Women
	≥625 μmol/L
	≥506 μmol/L
Bilirubin (total)	≥34.2 μmol/L
Hematology	
Hematocrit	Men
	Women
	<0.37 L/L
	<0.32 L/L
Hemoglobin	Men
	≤115 g/L

Test	Criterion value
Women	≤95 g/L
WBC counts	≤3 x 10  /L ≥20 x 10  /L
Eosinophils	≥10%
ANC	≤1 x 10  /L
Platelet counts	≤75 x 10  /L ≥700 x 10  /L
Urinalysis	
HGB	≥2 unit increase from baseline
Glucose	≥2 unit increase from baseline
Ketones	≥2 unit increase from baseline
Total protein	≥2 unit increase from baseline
Coagulation	
INR	>1.5

ALP=alkaline phosphatase; ALT=alanine aminotransferase; ANC=absolute neutrophil count AST=aspartate aminotransferase; BUN=blood urea nitrogen; GGT=gamma-glutamyl transpeptidase; HGB=hemoglobin; INR=international normalized ratio; LDH=lactate dehydrogenase; ULN=upper limit of normal range; WBC=white blood cell.

### 8.5.1. Laboratory Values Meeting Hy’s Law Criteria

All occurrences of possible drug-induced liver injury that meet Hy's law criteria as defined in the protocol Section 7.1.5.1 will be included in adverse events reporting.

### 8.5.2. Other Clinical Laboratory Tests

#### 8.5.2.1. Human Chorionic Gonadotropin Test

Serum beta-human chorionic gonadotropin (β-HCG) tests will be performed for all women of childbearing potential at screening. Urine pregnancy tests will be performed for all women of childbearing potential at the randomization visit, weeks 1, 2, and 3, and the EOT/early termination visit. Pregnancy test results will be listed.

#### 8.5.2.2. Follicle-Stimulating Hormone Test

Postmenopausal women will have a follicle-stimulating hormone (FSH) test at screening. Results will be listed.

### 8.6. Physical Examinations

Any physical examination finding that is judged by the investigator as a clinically significant change (worsening) compared with a baseline value will be considered an adverse event, recorded on the CRF, and monitored as described in Section 7.1.2 of the study protocol. Shifts

from baseline to weeks 4, 8, 12, and 24, and last on study assessment (double-blind and open-label) will be summarized using patient counts.

Descriptive statistics for weight and height will be provided.

### 8.7. Vital Signs

Summary statistics for vital signs (pulse, systolic and diastolic blood pressure, body temperature, and respiratory rate) will be presented at baseline, weeks 4, 8, 12, and 24, and last on study assessment (double-blind and open-label). Vital signs values and changes from baseline to each visit and last on study assessment will be summarized using descriptive statistics.

Summaries of potentially clinically significant abnormal values will include all postbaseline values (including scheduled, unscheduled, and early termination visits). The incidence of potentially clinically significant abnormal values will be summarized using descriptive statistics with the criteria specified in [Table 4](#).

[Table 4](#) specifies the criteria for identifying vital signs as potentially clinically significant abnormal values. Note that in order to qualify as potentially clinically significant abnormal, a value needs to meet both criteria below: ie, have a value beyond the criterion value and a change of at least the magnitude specified in the change relative to baseline column.

**Table 4: Criteria for Potentially Clinically Significant Vital Signs**

Vital Sign	Criterion value	Change relative to baseline
Pulse	≥120 bpm	Increase of ≥15 bpm
	≤50 bpm	Decrease of ≥15 bpm
Systolic blood pressure	≥180 mm Hg	Increase of ≥20 mm Hg
	≤90 mm Hg	Decrease of ≥20 mm Hg
Diastolic blood pressure	≥105 mm Hg	Increase of ≥15 mm Hg
	≤50 mm Hg	Decrease of ≥15 mm Hg
Respiratory rate	<10 breaths/min	
Body temperature	≥38.3°C	Change of ≥1.1°C

bpm=beats per minute

### 8.8. Electrocardiography

Any ECG finding that is judged by the investigator as clinically significant (except at the screening visit) will be considered an adverse event.

Shifts (normal and abnormal) from baseline to overall result interpretation, weeks 4, 8, 12, and 24, and last on study assessment (double-blind and open-label) will be summarized using patient counts. For overall result interpretation the worst postbaseline finding for the patient (the abnormal finding if there are both normal and abnormal findings) will be used in the summaries. Summary statistics for ECG variables will be presented at baseline, weeks 4, 8, 12, and 24, and last on study assessment (double-blind and open-label). Actual values and changes from baseline to each visit and last on study assessment will be summarized using descriptive statistics.

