7.7. Electrocardiography

A single 12-lead ECG will be recorded at the time points detailed in Table 4.

A qualified physician at a central diagnostic center will be interpreting the ECG. ECGs should be performed and transmitted according to the central ECG reading instructions provided in the ECG user manual. ECG equipment will be provided to all clinical sites. Although the ECG interpretation will be performed centrally, the clinical evaluation remains the investigator's responsibility.

Any unscheduled ECGs must also be submitted for central ECG reading.

All ECG results outside of the reference ranges will be judged by the investigator as belonging to one of the following categories:

- abnormal and not clinically significant
- abnormal and clinically significant

If results are abnormal, the ECG will be repeated 1 time.

The ECG will be evaluated by the investigator at the time of recording (signed and dated), and the printout should be kept in the source documentation file. When potentially clinically significant findings are detected by the investigator, a cardiologist should be consulted for a definitive interpretation. All communications and diagnoses should be filed in the source documentation file. The investigator's interpretation will be recorded on the eCRF regardless of the central reading interpretation. Any ECG finding that is judged by the investigator as

clinically significant (except at the screening visit [V1]) will be considered an adverse event, recorded on the source documentation and the eCRF and monitored as described in Section 7.1.2.

Objective alerts are predefined as described in the central ECG reading manual. In these cases, the site and the sponsor will be informed immediately.

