9.7. Safety Analysis

Safety analyses will be performed on the safety analysis set (Section 9.2.3).

Safety assessments and time points are provided in Table 4.

All adverse events will be coded using the Medical Dictionary for Regulatory Activities. Each patient will be counted only once in each preferred term or system organ class category for the analyses of safety. Summaries will be presented for all adverse events (overall and by severity), adverse events determined by the investigator to be related to test IMP (ie, reasonable possibility; see Section 7.1.4) (defined as related or with missing relationship) (overall and by severity), serious adverse events, and adverse events causing withdrawal from the study. Summaries will be presented by treatment group and for all patients. Patient listings of serious adverse events and adverse events leading to withdrawal will be presented.

Changes in laboratory, ECG, eC-SSRS, and vital signs measurements data will be summarized descriptively. All values will be compared with the predefined criteria to identify potentially clinically significant values or changes, and such values will be listed.

The use of concomitant medications will be summarized by therapeutic class using descriptive statistics. Concomitant medications will include ECT and all medications taken while the patient

is treated with IMP. Patients who begin prohibited therapies during the study will be discontinued from the study (eg, ECT, vagus nerve stimulation, direct current therapy, transcutaneous supraorbital stimulation, and other forms of electrical stimulation). Complete discontinuation criteria are provided in Section 4.3.

Safety data will be summarized descriptively overall, by treatment group, and by study phase. For continuous variables, descriptive statistics (n, mean, standard deviation, median, minimum, and maximum) will be provided for actual values and changes from randomization visit (day 1) to each time point. For categorical variables, patient counts and percentages will be provided. Descriptive summaries of serious adverse events and patient withdrawals due to adverse events will be provided as well.

If any patient dies during the study, a listing of deaths will be provided and all relevant information will be discussed in the patient narrative included in the CSR.

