## **5.6. Electrocardiography**

ECG findings (normal, abnormal not clinically significant, and abnormal clinically significant) at baseline will be summarized using descriptive statistics.

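### The ECG shift table in SAP 8.8 drops the clinical-significance grading that is collected and used at baseline, and the SAP does not say what becomes of the ECG criteria implied by Protocol 9.7

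*SAP*

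**What the plan says.** **Collection.** Protocol 7.7 states: "All ECG results outside of the reference ranges will be judged by the investigator as belonging to one of the following categories". The two categories are abnormal without and abnormal with clinical significance. The investigator's reading goes on the eCRF whatever the central reading says.

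**Baseline.** SAP 5.6 uses all three levels: "ECG findings (normal, abnormal not clinically significant, and abnormal clinically significant) at baseline will be summarized using descriptive statistics".

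**Post-baseline.** SAP 8.8 plans "Shifts (normal and abnormal) from baseline to overall result interpretation", and likewise to each scheduled visit and to the last assessment, separately for the double-blind and open-label periods. For the overall interpretation, "the worst postbaseline finding for the patient (the abnormal finding if there are both normal and abnormal findings) will be used in the summaries". SAP 8.8 also plans descriptive statistics for ECG values and their changes, and repeats the protocol's rule that a clinically significant ECG finding after screening is an adverse event.

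**Predefined criteria.** Protocol 9.7 says: "Changes in laboratory, ECG, eC-SSRS, and vital signs measurements data will be summarized descriptively". Its next sentence is: "All values will be compared with the predefined criteria to identify potentially clinically significant values or changes, and such values will be listed". The SAP supplies such criteria for laboratory tests (Table 3) and vital signs (Table 4). Its list of tables has none for ECG, and SAP 8.8 plans no count or listing of ECG outliers. SAP 11 declares no departure from the protocol's analyses, and the SAP Introduction gives the SAP precedence where the two documents differ.

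**The concern.** A shift table exists to show, by arm, who got worse relative to their own starting point. This one discards the distinction that separates a trivial change from an important one, although that distinction is already in the database and already shown at baseline.

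Patients with an abnormal baseline tracing are affected most. Exclusion criterion p (Protocol 4.2) keeps out anyone whose baseline ECG is judged clinically significant, so almost all abnormal baselines should be of the not clinically significant kind. The only worsening open to those patients is the one the table cannot display.

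The second issue is one of consistency. If Protocol 9.7 covers ECG, the SAP has left out a planned screen without saying so, and under its own precedence rule the omission takes effect. The protocol names cardiovascular effects as a theoretical risk of CGRP inhibition (1.3.1.2.2), schedules an ECG at every visit (Table 4) and has no data monitoring committee (5.10.3). The ECG tables should therefore be readable as they stand.

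**Working it through.** The plan gives no figure to reproduce here. The check is a count of table cells and a side-by-side reading.

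**1. What the two-level coding merges.** Write N for normal, A0 for abnormal without clinical significance and A1 for abnormal with it. Three levels give 3 × 3 = 9 baseline-to-post-baseline transitions; the SAP's two levels give 2 × 2 = 4 cells.

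| SAP 8.8 cell | Transitions it contains | Count |
|---|---|---|
| normal to normal | N→N | 1 |
| normal to abnormal | N→A0, N→A1 | 2 |
| abnormal to normal | A0→N, A1→N | 2 |
| abnormal to abnormal | A0→A0, A0→A1, A1→A0, A1→A1 | 4 |

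1 + 2 + 2 + 4 = 9. A0→A1 shares a cell with A0→A0 and reads as no shift.

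**2. After exclusion criterion p.** If no enrolled patient starts at A1, 2 × 3 = 6 transitions remain. Three are worsenings: N→A0, N→A1 and A0→A1. The planned table shows the first two as worsening but cannot tell them apart, and does not show the third at all. Neither transition that ends in a clinically significant finding can be identified.

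**3. The worst-finding rule.** It settles only the case of a patient with both normal and abnormal tracings. For a patient with both A0 and A1 after baseline it gives no order. Replacing the two levels by three without rewriting this rule would leave it incomplete.

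**4. How many patients.** The documents give no rate of abnormal baseline ECGs. Assuming 15% to 30%, purely for illustration, the abnormal-baseline rows would hold 340 × 0.15 = 51 to 340 × 0.30 = 102 patients. That is the size of the rows in which worsening cannot be displayed, not a number of events.

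**5. Whether extreme values would be hidden.** Take an assumed rise of 60 units in an ECG interval in 1 of 170 patients. The arm mean moves by 60/170 = 0.35 units, so the mean is insensitive. SAP 4.1, however, includes minimum and maximum among the descriptive statistics, and SAP 8.8 applies descriptive statistics to changes from baseline. If that rise is the largest in the arm, it appears as a maximum change of 60.

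**6. Criteria by data type.**

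| Data type | Named in Protocol 9.7 | Criteria in SAP |
|---|---|---|
| Laboratory | yes | Table 3 |
| Vital signs | yes | Table 4 |
| ECG | yes | none |
| eC-SSRS | yes | none; results listed (SAP 8.10) |

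Only for laboratory parameters does the protocol expressly leave such values to the SAP (7.4). Protocol 7.6 contains no such instruction for vital signs, yet the SAP supplies Table 4. The SAP has thus carried the 9.7 comparison beyond laboratory data and stopped before ECG without explanation.

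**The case against.** The strongest reply is that nothing important goes unrecorded. Any clinically significant ECG after screening is an adverse event. SAP 8.3 summarises adverse events by system organ class, preferred term and severity and lists them, and SAP 8.1 presents safety by treatment group and period. Because criterion p removes clinically significant baselines, nearly every later clinically significant finding is a worsening, so the adverse event tables should capture much the same patients. They rest on the same investigator judgment as the three-level grading, so a larger shift table adds no independent detection. All of this stands.

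A reader might infer that the plan would miss these events, or that ECG outliers are never screened. The documents do not support that. Besides the adverse event route and the planned minimum and maximum, Protocol 7.7 provides for individual alerts: "Objective alerts are predefined as described in the central ECG reading manual", with site and sponsor told at once. The most that can be said is that no criteria-based ECG analysis is specified in the SAP. Nor can those alerts be taken as the missing criteria: the manual is not among the documents, and Protocol 7.7 describes the alerts only as a means of notification.

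The reach of Protocol 9.7 is also open to argument. The sentence before the criteria comparison includes a questionnaire, the eC-SSRS, to which numerical criteria fit poorly. The protocol synopsis promises only descriptive summaries of ECG changes. That makes the screen less than certain, but Table 4 shows the sponsor did not confine it to laboratory data.

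Finally, ECG is not a listed safety endpoint (Protocol Table 3), and no clinically relevant ECG findings are reported from studies to date (Protocol 1.2.2.2). This lowers the stakes. It does not make the two-level table informative.

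**Conclusion.** The point holds as a defect of one safety table plus an unreconciled difference between the documents.

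The two-level coding folds nine transitions into four cells, presents a move to clinical significance from an abnormal baseline as no shift, and cannot separate minor from important change in patients who start normal. This follows from the text and needs no assumption about rates; it matters whenever any patient has an abnormal baseline ECG or a clinically significant finding later. The range of 51 to 102 patients rests wholly on the assumed 15% to 30%. No event is lost, and no efficacy result or error rate is touched.

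The Protocol 9.7 point rests on reading its reference to all values as covering the ECG data named just before. That is the natural reading, though not the only one. On it, SAP 11 is inaccurate in declaring no changes.

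The change is worth making because it is nearly free and uses data already collected.

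**What to change.** **SAP 8.8, shifts.** Tabulate every ECG shift (each visit, last assessment, overall interpretation) on the three levels of SAP 5.6. Define the worst post-baseline finding by the order clinically significant > not clinically significant > normal. The cost is a few words of SAP text and a 3 × 3 table in place of a 2 × 2. The downside is some sparse cells; the row for a clinically significant baseline should be nearly empty.

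**SAP 8.8 and SAP 11, reconciliation with Protocol 9.7.** Choose one:

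- Prespecify ECG criteria, with values set by the sponsor, and add an incidence summary by arm and period and a listing. This costs one criteria table, one summary and one listing, from existing data.
- State in SAP 11 that ECG values will not be compared with potentially-clinically-significant criteria, and give the reason. This costs a sentence or two.

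Neither step changes study conduct or patient management.

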## **8.9. Concomitant Medications or Therapies**

Concomitant therapies and medications, including medications that are taken on an as needed basis and occasional therapies, will be monitored during the study. Details of prohibited medications may be found in Section 5.7 of the study protocol. All concomitant medications will be coded using the WHO Drug.

The incidence of concomitant therapies and medications will be summarized using descriptive statistics by therapeutic class category and PT. Patients are counted only once in each therapeutic class and only once in each PT category. Concomitant therapies and medications will include all medications up to the end of study as defined in the study protocol.

The subset of concomitant pain medication and medication or therapy for migraine/headache will be summarized by the following indication categories.

- preventive medication from protocol appendix for migraine/headache
- opioids for migraine/headache
- NSAIDS for migraine/headache
- triptans for migraine/headache
- ergots for migraine/headache
- butalbital for migraine/headache
- medication from protocol appendix for other reason than depression
- benzodiazepines for other reason than anxiety/insomnia
- other

## **8.10. Electronic Columbia-Suicide Severity Rating Scale**

As part of the overall safety evaluation, the eC-SSRS will be used in conjunction with a qualified clinician's (ie, the investigator or a medically qualified person designated by the investigator) clinical judgment to assess the patient's suicidal ideation (severity and intensity) and behavior. The eC-SSRS Lifetime version will be completed by the patient at visit 1, and the eC-SSRS Since Last Visit version will be completed by the patient at all other time points.

The results from the eC-SSRS will be listed.

## **9. TOLERABILITY VARIABLES AND ANALYSIS**

Tolerability is summarized with patient disposition.

## **10. STATISTICAL SOFTWARE**

All data listings, summaries, and statistical analyses will be generated using SAS® version 9.4 or later.

## **11. CHANGES TO ANALYSES SPECIFIED IN THE STUDY PROTOCOL**

There are no changes to analyses specified in the study protocol.

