
Safety and tolerability objective (Secondary objective): To evaluate the safety and tolerability of monthly 225 mg sc and quarterly 675 mg sc fremanezumab in adult patients with migraine and MDD
	
 • occurrence of adverse events throughout the study • changes from randomization visit (day 1) in vital signs (pulse, systolic and diastolic blood pressure, body temperature, and respiratory rate) measurements • abnormal physical examination findings including body weight • use of concomitant medication for adverse events during the study • number (%) of patients who did not complete the study due to adverse events • occurrence of severe hypersensitivity/anaphylaxis reactions • suicidal ideation and behavior as suggested by eC-SSRS

CGI-S = Clinical Global Impression-Severity; eC-SSRS = electronic Columbia-Suicide Severity Rating Scale; HAM-D 17 = Hamilton Depression Rating Scale-17 items; HIT-6 = 6-item Headache Impact Test; MDD = major depressive disorder; MSQoL = Migraine-Specific Quality of Life; sc = subcutaneous.

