9.5.2. Secondary Endpoints

The key secondary efficacy endpoint is the mean change in depression symptoms from randomization visit (day 1) to week 8 after the first dose of study drug as measured by HAM-D 17.

Other secondary endpoints include the following:

- Number of patients with 50% or more reduction from the 28-day baseline period until 12 weeks after the first dose of study drug, in the monthly average number of migraine days
- Mean change in quality of life from randomization visit (day 1) to week 12 after the first dose of study drug as measured by the MSQoL questionnaire, role function-restrictive and role function-preventive domains
- Mean change from randomization visit (day 1) in disability score for overall impact, as measured by CGI-S and HIT-6, to the following time points after administration of the first dose of study drug:
 - weeks 4 and 8 (CGI-S)
 - week 12 (CGI-S and HIT-6)

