**Table 1: Primary and Secondary Study Objectives and Endpoints**

Objectives	Endpoints

Primary objective: To evaluate the efficacy of monthly 225 mg subcutaneous (sc) fremanezumab in adult patients with migraine and major depressive disorder (MDD)
	
Mean change in the monthly average number of migraine days from the 28-day baseline period during the 12-week period after the first dose of study drug

Key secondary objective: To evaluate the efficacy of monthly 225 mg sc of fremanezumab in adult patients with migraine and MDD on the reduction of MDD symptoms
	
Mean change in depression symptoms from randomization (day 1) to week 8 after the first dose of study drug as measured by:
 
 
• Hamilton Depression Rating Scale-17 items (HAM-D 17)
 

Secondary objective: To evaluate the efficacy of monthly 225 mg sc fremanezumab in adult patients with migraine and MDD in terms of responder rates in monthly migraine days
	
Number of patients with 50% or more reduction from the 28-day baseline period in the monthly average number of migraine days during 12 weeks after the first dose of study drug

Secondary objective: To evaluate the efficacy of monthly 225 mg sc fremanezumab in adult patients with migraine and MDD in terms of improving quality of life
	
Mean change in quality of life from randomization visit (day 1) to week 12 after the first dose of study drug as measured by:
 
 
• Migraine-Specific Quality of Life (MSQoL) questionnaire, role function-restrictive and role function-preventive domains
 

Fremanezumab at monthly doses of 225 mg sc, and placebo alternatively, in the 12-week double-blind treatment period

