## **6.3. Secondary Efficacy Endpoints and Analysis**

The key secondary efficacy endpoint is the mean change in depression symptoms from randomization visit (day 1) to week 8 after the first dose of study drug as measured by HAM-D 17.

Other secondary endpoints include the following:

- Number of patients with 50% or more reduction from the 28-day baseline period until 12 weeks after the first dose of study drug, in the monthly average number of migraine days
- Mean change in quality of life from randomization visit (day 1) to week 12 after the first dose of study drug as measured by the MSQoL questionnaire, role function-restrictive, role function-preventive, and emotional function domains
- Mean change from randomization visit (day 1) in disability score for overall impact, as measured by CGI-S and HIT-6, to the following time points after administration of the first dose of study drug:
  - weeks 4 and 8 (CGI-S)
  - week 12 (CGI-S and HIT-6)

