## 7. MULTIPLE COMPARISONS AND MULTIPLICITY

A fixed-sequence (hierarchical) testing procedure will be implemented to control the type 1 error rate at 0.05. The primary endpoint will be tested first at a type I error rate of 5%. If the analysis is statistically significant (p-value <0.05), then the key secondary hypothesis will be tested. If not statistically significant, confirmatory hypothesis testing will not be carried out on the remaining hypotheses. This process will repeat accordingly to the order of the secondary endpoints as specified in section 6.3. [REDACTED]

[REDACTED]

[REDACTED]

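### SAP 11 reports no changes from the protocol, yet eC-SSRS falls from a summary to a listing and MSQoL Emotional Function enters the secondary test order

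*SAP*

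**What the plan says.** SAP 11 consists of one sentence: "There are no changes to analyses specified in the study protocol".

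**eC-SSRS.** Protocol Table 3 (section 2.1) names among the safety endpoints "suicidal ideation and behavior as suggested by eC-SSRS". Protocol 9.7 says "Changes in laboratory, ECG, eC-SSRS, and vital signs measurements data will be summarized descriptively", and adds that safety data are summarized overall, by treatment group and by phase. SAP 8.10 says "The results from the eC-SSRS will be listed" and plans nothing further.

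**MSQoL.** Protocol 9.5.2 defines the secondary endpoint by the "MSQoL questionnaire, role function-restrictive and role function-preventive domains". SAP Table 1 agrees: "Migraine-Specific Quality of Life (MSQoL) questionnaire, role function-restrictive and role function-preventive domains". SAP 6.3 instead has "MSQoL questionnaire, role function-restrictive, role function-preventive, and emotional function domains", placed ahead of CGI-S and HIT-6. SAP 7 then takes its testing order from that list: "This process will repeat accordingly to the order of the secondary endpoints as specified in section 6.3".

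**Lesser items.**
- Protocol 9.5.4 names the ITT set for efficacy, in a sentence that cites the ITT, mITT and PP sections together. SAP 6.1 uses the mITT sets for all efficacy analyses; SAP 3.1.2 requires at least one dose and 10 post-randomization days of primary-endpoint (diary) data.
- Protocol 5.7 promises the percentage of patients whose antidepressant or preventive medication changed. SAP 8.9 gives medication incidence only.
- Protocol 9.4.2 plans between-group tests of baseline variables. SAP 5.3 gives descriptive summaries.

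**The concern.** A reader who relies on SAP 11 would look for no departures from the protocol.

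- **Suicidality by arm.** All patients have MDD and a PHQ-9 of at least 10, and there is no data monitoring committee. The randomized comparison of suicidal ideation and behaviour would rest on reading a listing, plus whatever was recorded as an adverse event. Under protocol 7.1.1, worsening depression becomes an adverse event only if it exceeds the expected course for that patient, so adverse event tables cannot be assumed to stand in for the scale.
- **The confirmatory order.** In a fixed sequence, every hypothesis is a gate for those after it. A domain that is not a secondary endpoint in the protocol or in SAP Table 1 would stand in front of CGI-S and HIT-6, which are secondary endpoints in the protocol.
- **Analysis set.** HAM-D 17, MSQoL, CGI-S and HIT-6 are collected at visits, but a patient's inclusion would depend on diary keeping.

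**Working it through.** **1. The plan's own figures.** With 144 per group and two-sided alpha 0.05, power = Φ(Δ / (σ√(2/n)) − 1.96).
- Migraine days: 2 / (5.2 × √(2/144)) = 3.264; Φ(1.304) = 0.904, against 90% stated.
- HAM-D 17: 2 / (6 × √(2/144)) = 2.828; Φ(0.868) = 0.807, against about 80% stated.
- Randomized number: 288 / 0.85 = 339, against about 340 stated.

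All reproduce, and nothing below changes them.

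**2. eC-SSRS.** The comparison is textual: summary in protocol 9.7, listing in SAP 8.10, and no table in any visible SAP section. For scale, with 170 per arm, a table would bound a zero count at 1 − 0.05^(1/170) = 1.75% (one-sided 95%). It would show an illustrative 9/170 as 5.3% (exact 95% CI 2.4-9.8%). The 9 is invented for illustration.

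**3. Number of tests.** Count the primary, HAM-D 17, responder, each MSQoL domain, CGI-S at three visits, and HIT-6.
- Two domains: 1 + 1 + 1 + 2 + 3 + 1 = 9.
- Three domains: 1 + 1 + 1 + 3 + 3 + 1 = 10.

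SAP 6.3.3.2 analyses the three domain scores, Appendix E scores them independently, and no MSQoL total is defined. Emotional Function is therefore an added test.

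**4. Chance that the added test blocks CGI-S and HIT-6.** The order taken is primary (power 90%, from the plan), HAM-D 17 (80%, from the plan), responder (90%, assumed), Restrictive, Preventive, Emotional Function (each with assumed power p). Under independence, P(reached and fails) = 0.9 × 0.8 × 0.9 × p² × (1 − p). The correlated rows come from 2,000,000 simulated trials per setting.

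| Setting | p = 70% | p = 80% | p = 90% |
|---|---|---|---|
| Independent | 9.5% | 8.3% | 5.3% |
| Correlation 0.6 within MSQoL, 0.3 otherwise | 5.0% | 4.0% | 2.3% |
| Correlation 0.8 within MSQoL, 0.5 otherwise | 3.4% | 2.5% | 1.3% |

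Responder power of 80% or 95% instead of 90% widens the overall range to 1.1-10.1%. With CGI-S power of 80% (assumed), blocking costs a CGI-S test that would have passed in 4.2-7.6% of trials under independence and 1.0-4.2% under correlation.

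**5. mITT and the non-diary scales.** The first post-baseline visit is week 4, and SAP 4.4 keeps early-termination data out of by-visit summaries. Most patients who leave with fewer than 10 diary days would have no week-4 score in any set. The rule matters only for patients who attend week 4 or later with fewer than 10 diary days. For someone completing 12 weeks that means under 10/84 = 11.9% of days, after 21 of 28 were required at entry. If k excluded patients in one arm each differ by 6 points (one planned SD), the arm mean moves by about 6k/144: 0.04 points for k = 1 and 0.5 points for k = 12. Twelve patients is 12/144 = 8.3% of an arm, and 0.5 is a quarter of the planned 2-point difference. That is a deliberate extreme; the documents give no exclusion count.

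**The case against.** **Precedence.** The SAP Introduction lets the SAP prevail and leaves differences to the clinical study report, and protocol 9.10 allows several places for recording deviations. This stands as permission to differ. It does not make a flat denial of changes true. Nor can it settle SAP 6.3 against SAP Table 1, where the SAP disagrees with itself.

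**eC-SSRS.** The protocol synopsis omits the scale from its summary sentence, the listing covers every patient, SAP 8.3 tabulates adverse events, and SAP 5.2 counts withdrawals by reason. The data are indeed not lost, but protocol 9.7 is the full text and no by-arm count of the scale is planned. A reader might infer that suicidality goes unmonitored. The documents do not support that: protocol 7.8 requires evaluation by a psychiatrist of any positive finding on the since-last-visit version. The gap is in the analysis.

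**Test order.** The powers beyond the first two endpoints and all correlations are assumed, and independence between domains of one questionnaire is implausible. SAP 7 is redacted just after the order sentence. All of this stands, so the lower range is the more credible one and domain-by-domain testing remains an inference. A reader might also infer inflated type I error. Adding a hypothesis to a fully ordered sequence does not inflate it.

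**Analysis set.** Protocol 9.5.4 cites three sections with the word respectively, which suggests that the mITT and PP names were dropped in drafting. Protocol 9.2.2 already defines mITT with the same 10-day condition. SAP 6.1 may therefore be correcting an error. A reader might infer that the key secondary analysis is biased; no bias is shown.

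**PP set.** The 75% diary rule and the exclusion of wrong-drug patients could be read as new. They mostly make explicit what protocol 6.1.1, 9.2.4 and Appendix C already imply, and should not be presented as clear changes. The change of base set from ITT to mITT is the plain difference.

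**Conclusion.** The SAP 11 statement is incorrect, and two of the differences it passes over should be fixed.

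- **eC-SSRS** is the firmest, because it needs no assumption: a named safety endpoint loses its promised summary.
- **Emotional Function** is a firm contradiction between SAP 6.3 and both SAP Table 1 and protocol 9.5.2. Its practical cost is modest: about 1-5% of trials with correlated endpoints, and up to about 10% under independence. This is conditional on sequential testing of the domains and on the assumed powers.

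The rest is minor. Any mITT effect on the non-diary scales is probably very small. The medication-change percentage is an omission from the visible SAP. The dropped baseline tests are presentational. One further item needs a sentence of reconciliation: protocol 9.2.1 includes data after treatment discontinuation, while SAP 1.3 applies hypothetical strategies to early discontinuation. Diary entries stop at the early-withdrawal visit, so this concerns mainly patients who stop study drug but stay in the study. None of this invalidates the primary analysis or alters sample size or alpha.

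**What to change.** Before unblinding:

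- **SAP 8.10:** add n (%) of patients with post-baseline suicidal ideation and with suicidal behaviour, by treatment group and period.
- **SAP 6.3:** remove Emotional Function from the confirmatory list to match SAP Table 1, or report it after HIT-6 as non-confirmatory.
- **SAP 6.1:** analyse HAM-D 17, MSQoL, CGI-S and HIT-6 in all randomized patients with available post-baseline values, as randomized; keep the 10-day rule for diary endpoints. This set is not identical to the protocol's ITT set, so it should be declared too.
- **SAP 8.9:** add n (%) by treatment group with a change in antidepressant or migraine preventive medication.
- **SAP 11:** replace the sentence with a short list of the differences that remain: the efficacy analysis sets, the PP base set, the omitted baseline tests, and how the post-discontinuation data of protocol 9.2.1 fit the hypothetical estimand.

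The cost is SAP wording and two short tables from data already collected.
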